### 6.4. **Accountability Procedures for the Study Intervention/Investigational Product(s)**

The study drugs will be shipped from the supplier directly to the IRSS in Burkina with all appropriate permits and documentations. They will be transported to the drug stock room at the field site, accounted for by the unblinded study pharmacist, dispensed as described in 6.2 above in containers labeled per village and in accordance with the blind, and distributed to the clinical team no more than 2 days prior to their administration by the clinical team.

The Investigator is responsible for ensuring that a current record of product disposition is maintained and product is dispensed only at the study site by authorized personnel. Records of product disposition, will consist of the date received, date administered, quantity administered, and the subject number to whom the drug was administered.

The unblinded study pharmacist will be responsible for maintaining accurate records of the shipment and dispensing of the investigational product. The pharmacy records must be available for inspection by the CRO at any time.

---

Unused investigational product will be stored in the designated climate-controlled study drug storage room <30°C and free from high humidity in the Investigational Pharmacy until clinical trial accountability is completed. At study termination, all unused investigational product will be disposed of in accordance with the manufacturer's operation protocol following complete drug accountability and monitoring.

## 6.5. **Assessment of Subject Compliance with Study Intervention/Investigational Product/Investigational Device**

The clinical team will distribute the drugs door-to-door at the same time as the CHWs distribute the SMC door-to-door to the village children, at the beginning of each treatment round month (July, August, September, October) in two consecutive seasons. Treatment with the study drugs will be via DOT/NDOT, and unused drug will be returned to the pharmacist after each MDA. Administration will be documented on the CRFs in the nurse tablets.

## 6.6. **Concomitant Medications/Treatments**

No medications are restricted on the Iver P and Mectizan package inserts, so none will restrict treatment eligibility. All concomitant medications known to be taken during the study by study participants will be recorded in the appropriate sections of the CRF with indication, dose information, and dates of administration.

However, due to potential CYP3A4-mediated drug-drug interactions, participants in the PK/PD sub-study will not be eligible if they have received any of the following medications within 14 days of IVM administration:

- Carbamazepine
- Clarithromycin
- Erythromycin (oral)
- Ketoconazole
- Phenobarbital
- Phenytoin
- Rifabutin
- Rifampin
- Halofantrine
- Any other medication known to significantly affect CYP450 metabolism.

---

## 7. STUDY SCHEDULE

### 7.1. Recruitment

Malaria-endemic villages in southwestern Burkina Faso that will participate in SMC in season 1 of the study will be recruited to participate. Small to medium size villages ranging between 200-500 people will be recruited; per our power analysis, we require 7 villages per arm and ~100 children who are  $\leq 10$  years of age per cluster.

Recruitment will follow the procedures performed during RIMDAMAL I, whereby prospective areas in Southwest Burkina Faso from which villages could be recruited will be identified by consultations between the IRSS regional director ([name]) and scientists, and the national and regional health authorities at the Burkina Faso MoH. Primary considerations will be whether or not SMC is ongoing in the prospective areas, whether other scientific or clinical studies in the prospective areas are planned or ongoing, and whether other malaria control and/or NTD control interventions (e.g. IRS, MDA with albendazole or azithromycin) are planned or ongoing in the prospective areas.

Once an ideal study area is targeted for recruitment, we will obtain spatial maps and visit the area to understand the layout of villages, and make lists of ideal villages to recruit. We will attempt to choose villages that have distinct boundaries and non-populated buffer zones of agricultural fields or bush land surrounding them in order to minimize mosquito movement between control and intervention clusters and between study and non-study villages.

Subsequently, [name], other scientists of the IRSS, and regional health authority officers will approach the village chiefs, elders and CHWs, and describe the study to them and answer any questions they may have in an open meeting in the village. If these village leaders give their consent to proceed recruiting the village populace, a subsequent public meeting of all the heads-of-households in the village may be planned to again describe the study, and further answer any questions they may have. Upon gaining these community consents, randomization/allotment will occur at the public event described in section 5.3.1, and following that, screening and enrollment will begin.

## 7.2. Screening

Once community consent is affirmed and randomization/allotment occurs, screening, consent and enrollment will proceed with individual participants in each study village. The study investigators will travel to each village and meet publicly with the heads-of-households to re-inform them of the study goals and objectives, of the process of the public randomization event, and the intervention procedures that will occur with family members in their own households. These interventions include the data and sample collection procedures. The heads-of-households will be reminded of the need for them and their family members to be present for any subsequent interventions in their village, and of the active case surveillance in any children of theirs which may be enrolled in the active case detection (ACD; referring to children who will be regularly checked for malaria cases/episodes by the clinical team) cohort.

The administration of the interventions will proceed at the beginning of the months designated by the regional health authorities for SMC round administrations (July-October in each intervention phase season). As the intervention proceeds, if the status of any individual changes regarding their eligibility to is more standard participant in the intervention (e.g., an allergic response to the study drug is determined), this information will be recorded on the case report form and flagged for the subsequent IVM MDAs. In the case of pregnancy, since this is contra-indicated for IVM treatment, all women of possible child-bearing age (ages 12-45 or still not had menopause) will be screened using a pregnancy urine rapid test (e.g. SD Bioline hCG) in the week prior to each IVM MDA, and if positive, they will be excluded from the MDA.

## 7.3. Enrollment/Baseline

All persons who live in each study village and who do not have a permanent disability or serious medical illness that prevents or impedes study participation and/or comprehension will be asked to enroll. Once a head-of-household signs his/her household consent document (appendix VII), the investigators will engage all the members of each household, take a census of the inhabitants, conduct a questionnaire of inhabitants, survey the houses, and enroll adults  $\geq 18$  years of age with their written consent. Enrollment of children between 12-17 years of age will also be gained by obtaining their written assent, and children  $<12$  years of age by obtaining the written consent of their parent/guardian. All consents and assents will be obtained in the presence of a community witness, who will sign his or her name to these documents. Members of the study team will subsequently map the household and house locations in the village. Screening and participant information will be recorded on eCFRs on tablets, and individual participant exclusions/inclusions for participating in the intervention will be recorded (see 5.1).

### 7.3.1. PK/PD cohort

PK/PD cohort children will be chosen from one control and one intervention village, using the arm code so as not to break the blind. They will be subject to follow-up at an increased frequency. Enrollment criteria are otherwise as for the ACD cohort, with additional exclusion criteria of a 1) hemoglobin <7 g/dL (done by Hemocue or other instrument), and 2) use of concomitant medications (Section 6.6). The total number of participants in the PK/PD cohort is n=180 and participants will be age-stratified. Up to one individual may be enrolled from each age strata within the same household:

- 5-10yo (n=60, 30 from each village-arm)
- 11-18yo (n=60, 30 from each village-arm)
- $\geq 19$ yo (n=60, 30 from each village-arm)

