difference in the rates between the arms with 80% power. The primary outcome will be analyzed as intention-to-treat, meaning it will include all enrolled cohort children ( $\leq 10$  years old) in the groups to which they were randomly assigned, regardless of their compliance with the entry criteria, regardless of the treatment they actually received, and regardless of subsequent withdrawal from treatment or deviation from the protocol. Importantly, all eligible cohort children ages 3-59 months are expected to receive SMC, and all eligible cohort children  $\geq 90$  but not taking SMC are expected to receive either ivermectin or placebo as the intervention. However all these children, no matter their treatment, will be included in the primary outcome analysis. The incidence of episodes from the children cohort will be used as the primary measurable outcome to evaluate the impact of the intervention when compared to the control arm. The primary analysis will use either cluster-level analyses, or multilevel/hierarchical regression modeling techniques to account for clustering at the level of the randomization unit (village), as well as analyze individuals with multiple time points where both unadjusted and adjusted analyses will be performed. The unadjusted as well as adjusted estimates depicting the impact of the intervention versus control will be reported along with 95% confidence intervals. The time-to-first infection will also be analyzed using a survival analysis within each arm and calculation of a hazard ratio with 95% confidence interval. Secondary data generated from Aim 1 will include adverse events (AE) and serious adverse events (SAE). The risk of SAE and AE will be compared between intervention and control arms by calculating risks ratios and attributable risks with 95% confidence intervals. Standard statistical hypothesis testing, as well as estimating the effect sizes and confidence intervals, will be used to measure the differences in entomological, parasitological, and pharmacokinetic secondary outcomes between arms and the exploratory outcome measures.

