## 5.3. Treatment Assignment Procedures

### 5.3.1. Randomization Procedures

This will be a cluster (village)-randomized trial. Once the chiefs/leaders and heads-of-households of all fourteen selected villages give their verbal consent to participate following informational and question and answer meetings with the study team, a village representative and the CHWs representing each village will be asked to participate in a public randomization event at the facilities of the district health authority, attended by the district medical director and members of the study team. In front of the attendees, the numbers “1” and “2” will be written on 7 cards each, which will be sealed in identical opaque envelopes, mixed in a container, and then randomly pulled from the container by each village representative. Villages will be assigned to the arm written on the card selected by this representative, and the procedures will be video recorded. These arm designations will be linked to the masked active ingredient tablet or placebo (below).

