#### 7.10.1.1. PK/PD cohort

Participants in the PK/PD will be subject to capillary PK sampling up to 5 time points from the following sampling times 0 (pre-last dose), 1, 4, 8, 12, 24, 48, 52, 60, 72 hours, and on day 7, 14, 21, and 28. At up to 3 time points, simultaneous capillary and venous samples will be taken to assess the correlation between concentrations in these matrices, enabling us to compare our data with previous studies, and inform our mosquito-based studies. Clinical laboratory safety monitoring (5 mL venous draw) will also be conducted on days 0 (pre-IVM), day 14, and day 28 in all PK/PD participants, which will entail a complete blood count (CBC) with differential, liver enzymes (alanine aminotransferase (ALT) and aspartate aminotransferase (AST)), and creatinine (Cr).

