5. APPENDIX: FUTURE WORK TO BE CONSIDERED

- 1. Pharmacokinetic/dynamic parameters
 - a. Impact of age on IVM PK
 - b. Evaluation of IVM metabolites
 - c. Relationship of IVM PK with blood-feeding results done at CSU
 - d. Safety of IVM (clinical, hematology, chemistry)
 - e. Comparison on capillary and venous measurements of IVM

2. Parasite data

- a. Parasitemia [Count data] done by quantitative PCR compare (log10) distributions in populations between arms
 - i. SMC-treated only
 - ii. IVM/placebo-treated only
 - iii. all cohort
- b. Multiplicity of Infection (MOI) per episode or sampling timepoint and molecular Force of Infection (mFOI) per child [Count data] done by either genotyping microsatellites or amplicon deep sequencing
 - i. Regression analysis with Poisson distribution, in an unadjusted analysis followed by an adjusted analysis taking into account the random effects of the cluster (village) and household and fixed effects such as sex, LLIN use, age, and treatment with SMC or IVM.

3. Entomology data

- a. Survivorship bioassays of blood fed mosquitoes [Survival assays]
 - i. Consider time variable
- b. Catch density [count data]
 - i. Consider time variable
- c. Age structure
 - i. Age distribution of mosquitoes in Intervention vs. Control clusters
 - ii. Proportion of mosquitoes caught over an age cut-off (>10 days)
 - 1. Consider time variable
- d. Proportion of mosquito blood meals taken from humans vs other animals
 - i. Consider time variable
- e. Proportion of mosquitoes with sporozoites
 - i. Consider time variable
- f. Entomological inoculation rates (human biting proportion x sporozoite rate)
 - i. Consider time variable

4. Other studies

- a. Impact of IVM on the prevalence of drug and insecticide resistance
- b. Impact of IVM on all-cause anemia in children
- c. Household survey association of household factors and vector density

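### Protocol Section 4 plans between-arm tests of pharmacokinetic outcomes, but the PK/PD cohort has one village per arm, so arm and village cannot be separated there

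*Protocol*

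**What the plan says.** **Design.** Protocol Section 5.3.1: "This will be a cluster (village)-randomized trial". Section 7.3.1: "PK/PD cohort children will be chosen from one control and one intervention village". That sentence says children, but the strata listed under it run from age 5 to adults, so the two-village sampling covers all ages. On size: "The total number of participants in the PK/PD cohort is n=180 and participants will be age-stratified", with the first stratum given as "5-10yo (n=60, 30 from each village-arm)" and the other two the same.

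**Planned comparison.** Section 4 says that standard hypothesis tests, effect sizes and confidence intervals "will be used to measure the differences in entomological, parasitological, and pharmacokinetic secondary outcomes between arms". It makes no exception for a cohort with one village per arm.

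**What the cohort supplies.** Section 3.2.2 includes in the PK/PD outcome the survival of blood-fed mosquitoes caught in participants' houses. Section 7.10.1 plans no formal clinical laboratory work outside this cohort. Within it, "Clinical laboratory safety monitoring (5 mL venous draw) will also be conducted on days 0 (pre-IVM), day 14, and day 28", covering blood count, ALT, AST and creatinine.

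**Other statements on PK.** The PK hypothesis in Section 10.1 concerns change over time and variation by age and gender. Section 10.4 names only entomological and parasitological outcomes for between-arm testing. The SAP places PK in its appendix of future work. Item 1d there reads "Safety of IVM (clinical, hematology, chemistry)" and gives no method.

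**The concern.** In this cohort, knowing a person's village is the same as knowing the arm. A p-value or interval comparing the two groups says whether two villages differ. It does not say whether ivermectin made the difference, and no covariate or random effect can separate the two.

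The consequence depends on the outcome. The placebo village receives no study ivermectin, so an arm contrast in drug concentration has an obvious answer and misleads nobody. Mosquito survival and laboratory values differ in this respect. Two villages may differ in vector species, malaria burden or anaemia, and such a difference could pass for a drug effect or hide one. These are also the only scheduled blood count, liver enzyme and creatinine data in the trial, and Section 8.5 allows monitoring-board reports to include laboratory values and to be presented by arm.

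**Working it through.** **1. Cohort size.** Three age strata × 30 per village-arm × 2 villages = 180, which agrees with Section 7.3.1. Each village supplies 3 × 30 = 90.

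**2. Information about village variation.** Two villages less two arm means leaves 2 − 2 = 0 degrees of freedom. Two allocations are possible, so the smallest two-sided permutation p-value is 2/2 = 1.0.

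**3. The protocol's own cluster formula.** Section 10.2 uses the unmatched rate formula c = 1 + (z_α/2 + z_β)² × [(λ0 + λ1)/y + k²(λ0² + λ1²)]/(λ0 − λ1)². Its inputs are λ0 = 1.088, λ1 = 0.619, k = 0.258, y = 48, two-sided α = 0.05 and 80% power.
- Bracket: 1.707/48 + 0.0666 × 1.567 = 0.0356 + 0.1043 = 0.1399.
- Divided by 0.469² = 0.2200: 0.636.
- Multiplied by 7.849 and with 1 added: c = 5.99.

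This reproduces the stated 6 clusters per arm for the primary outcome. Setting c = 1 requires the bracket to be zero, that is, no variation at all. The method the trial uses to size itself has no solution at one village per arm.

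**4. Error rate if village is ignored.** Design effect = 1 + (m − 1) × ICC. Actual two-sided error of a nominal 5% test = 2 × [1 − Φ(1.96/√design effect)]. The documents give no ICC for PK, laboratory or mosquito outcomes, so a range is shown. The value 0.059 is the ICC calculated from the earlier trial's data (Section 10.2), and using it here is an assumption.

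| ICC | Design effect, 90 v 90 | Error, 90 v 90 | Design effect, 30 v 30 (one stratum) | Error, 30 v 30 |
|---|---|---|---|---|
| 0 | 1.00 | 5% | 1.00 | 5% |
| 0.01 | 1.89 | 15% | 1.29 | 8% |
| 0.02 | 2.78 | 24% | 1.58 | 12% |
| 0.059 | 6.25 | 43% | 2.71 | 23% |

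The loss of identifiability in step 2 does not depend on the ICC. Only the size of the error in step 4 does.

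**5. Consistency of the documents.** Section 4 tests PK between arms. Section 10.4 carries an almost parallel sentence without PK. Section 10.1 and the outcome definition in Section 3.2.2 compare PK over time and across strata. The SAP specifies no arm comparison for PK. Section 4 is the exception.

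**The case against.** The best reply is that the problem rests on one word in a general sentence. The specific sections do not repeat it, and the stated purpose of the cohort is to link drug concentration to mosquito feeding and survival, which needs no arm contrast. The test that the sentence literally names, on drug concentration, does no harm. All of this stands, and it limits the point to a correction of Section 4 and a guard on how the cohort's other data are reported.

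Three stronger readings are tempting, and the documents do not support them.

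- *A reader might infer that a between-arm laboratory safety test is planned.* Section 7.10.1.1 describes monitoring only, and item 1d of the SAP appendix is a topic without a test. A comparison by arm is foreseeable but not specified.
- *A reader might infer that the trial's anaemia result depends on these two villages.* SAP 2.3.1.2 compares anaemia in the active case detection children and in cross-sectional households of intervention and control villages, not in this cohort.
- *A reader might take 43% as the expected error rate.* It requires an individual-level test that ignores village and a borrowed ICC. The ICC for change from day 0 may also differ from that for levels. Day-0 samples exist, and analysing change removes stable village differences, though not those that arise during follow-up.

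The objection does not rescue the arm contrast. A valid test would need village variance to be assumed zero or imported from elsewhere, and the documents supply no such variance for these outcomes.

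**Conclusion.** The point holds in limited form. Section 4 calls for a between-arm analysis that the PK/PD cohort cannot support, because it has one randomized village per arm, and it disagrees with Sections 10.1 and 10.4 and with the SAP. The conclusion that no valid arm test or interval exists in this cohort follows from the design alone. The error rates (5% to 43% over ICCs of 0 to 0.059 for 90 v 90) are illustrations that rest on an assumed ICC and on village being ignored.

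The practical exposure is confined to survival of mosquitoes from cohort houses and to the cohort's laboratory values, if either is compared by arm. The primary analysis, the trial-wide adverse event and entomology comparisons, and the anaemia comparison are not affected. Nor are the within-treated PK analyses over time and across strata invalid, although they describe a single treated village.

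**What to change.** 1. In Protocol Section 4, delete the word *pharmacokinetic* from the sentence on between-arm testing. This brings it into line with Sections 10.1 and 10.4.
2. State in the protocol and in the SAP appendix that PK/PD inference is made within the ivermectin village: concentration over time, by age and sex, and against mosquito survival, with participant and house as random effects. Add that it rests on one treated village.
3. Report this cohort's laboratory changes from day 0, and its mosquito survival, descriptively by arm, with no between-arm p-value or confidence interval for a drug effect.

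The cost is wording in two documents and the loss of a formal arm contrast in this cohort, which the design could not have supported. If such a contrast is wanted, the cohort must span several villages per arm. An exact two-sided permutation test cannot fall below 0.05 with three per arm (2/20 = 0.10) but can with four (2/70 = 0.029). That would be a change of design with field costs, not an edit.

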### 7.4. Follow-up

Active case surveillance will be conducted by study nurses visiting each enrolled ACD cohort child weekly following the start of the first MDA and ending 30 days following the last MDA of the season. At each visit, the nurse will record patient information in the CRF, measure axillary temperature, take a blood sample (for the RDT, slide and filter paper) if indicated, and treat with AL if an uncomplicated malaria episode is confirmed by the RDT. Any other treatment (e.g., paracetamol) will be in consultation with the study physicians.

All episodes of malaria will be classified as uncomplicated or complicated based on the following criteria:

Uncomplicated malaria (all the following must be present)

- 1) Fever ( $> 37.5^{\circ}\text{C}$ ) or history of fever in the previous 24 hours
- 2) Positive RDT
- 3) Absence of complicated malaria

Complicated malaria (any of the following)

- 1) Evidence of severe malaria (see Appendix D) and parasitemia
- 2) Parasite density  $> 500,000/\mu\text{L}^*$

\* Note that clinical decisions are made by RDT. However, if a nurse/doctor requests a blood smear to be read urgently, this will be performed. If the parasite density is above this threshold in this instance, the participant will be treated as having severe malaria.

During these visits, the nurse will inquire about, and record in the CRF, any AEs spontaneously communicated by the rest of the enrolled village populace (passive surveillance), and treat them as able in consultation with the study physicians or refer them to the district health clinic or hospital. Complicated malaria or other SAE will be referred to the district hospital immediately. Interim safety and efficacy analyses will be performed in the middle of season 1 (between the 2nd MDA and the 3rd MDA) and in between the two intervention phase seasons, and presented to the DSMB as described in 9.5.

In addition to the active case surveillance by the study nurses, entomology teams will periodically sample mosquitoes from households in the village during each season, and members of the parasitology team or the nurses will take a finger blood sample from all cohort children and a subset of enrolled adult participants at cross-sectional time points each season.

